13.4 EVALUATION OF SECONDARY OUTCOME VARIABLES

Secondary outcomes: To gather preliminary information about the efficacy of the experimental treatment in terms of combined MRI activity, incidence of relapses and disability progression.

- The total number of GEL lesions at MRI at weeks 4, 12 and 24 in the group originally randomised to placebo will be compared with the number of GEL lesions at MRI at weeks 28, 36 and 48 following the infusion using a mixed effect generalised model with NB errors.
- The dependence on time of the total number of GEL at MRI will be analysed in the group originally randomised to active treatment using a mixed effect generalised model with NB errors.
- Combined unique MRI activity (new or enlarging T2, or enhancing or re-enhancing lesions). The total number of new or enlarging T2, or enhancing or re-enhancing lesions at MRI at week 4, 12 and 24 post-treatment will be recorded in the two groups using a Negative Binomial (NB) regression analysis with the treatment group as covariate.
- Number of relapses in MSCs treatment group vs. placebo group will be acquired and using a Negative Binomial (NB) regression analysis with treatment group as covariate
- Time to sustained progression of disability (RRMS group) will be analyzed with a Cox proportional-hazards model
- Proportion of progression-free patients in two groups will be compared with the use of a chi-square test (RRMS patients).
- Mean changes in Multiple Sclerosis Functional Composite (MSFC) score in MSC treatment group vs. placebo group compared to baseline will be analysed with a one-way ANOVA test.

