5.2.4. Rationale for this study

Evidence from preclinical studies suggested that MSCs were an effective cell therapy for experimental autoimmune encephalomyelitis (EAE). In EAE, the IV injection of MSCs ameliorates the clinical course of acute disease and decreases demyelination, immune infiltrates and axonal loss, but has little or no effect in later stages of EAE. These results led to the conclusion that MSC administration should focus on individuals with on-going inflammation and before they develop irreversible disability. Pioneer small clinical studies in MS have already suggested their safety, thus paving the road from their clinical exploitation into larger phase II studies addressing their biological effect on markers of disease activity [39]. An international panel of MS neurology and stem cell experts, as well as immunologists formed an “International Mesenchymal Stem Cells Transplantation” (MSCT) Study Group with the aim to derive a consensus on the utilisation of MSCs for the treatment of MS along with protocols for the culture of the cells and the treatment of patients. This international consensus, based on the efforts of [name] (University of Genoa) and [name] (University of Ottawa), has been achieved and was published in 2010 [42]. In the consensus paper, the authors devised the synopsis of a phase I/II clinical trial, which will be fully adopted by scientists and clinicians belonging to the MSCT Study Group and presented to the respective national regulatory and funding agencies as single nation studies. This approach will enable the running of a series of parallel, independent but related, national studies adopting identical protocols, inclusion and exclusion criteria, primary and secondary outcomes collected on identical forms. The opportunity to pool the results of these studies will overcome the limitations of small phase I/II studies and provide enough statistical power to draw conclusions on the safety and efficacy of autologous MSCs transplantation in MS [42]. Our study will be conducted following the guidelines of the aforementioned consensus and utilise a protocol identical to the one adopted in other European countries and North America participating in this international collaborative effort. Identical, parallel but independent national trials will be conducted in Spain, Sweden, Denmark, France, Germany and Canada in order to assess the efficacy, safety and the toxicity of MSC infusion, as administered within this specific treatment protocol, in active MS. Evaluation of primary and secondary outcomes as well as exploratory outcomes will be carried out at the single national trial level but, more importantly, also on the entire data set obtained by pooling the results of all national trials, for an expected total of 160 randomised patients.

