This is a virtual visit not requiring patient attendance and defines a time point for MSC release. If the manufactured MSC product is released for clinical use, subjects will be eligible to continue in the study.

Week 0

Subjects will have the following performed:

- An MRI will be carried out **prior to** infusion of the study treatment (section 12.8).

Subjects will then be admitted as a day case to Hammersmith Hospital.

- Inclusion/exclusion criteria will be reviewed especially to confirm that inclusion criteria 6 is fulfilled.
- Concomitant medications will be recorded.
- Adverse events will be recorded.
- The patient will undergo a full physical examination including vital signs.
- Blood will be taken for haematological and clinical chemistry parameter measurement.
- Pregnancy testing will be performed (if applicable).
- 80 ml blood research samples will be taken.*
- A Mantoux test will be performed.
- Urinalysis will be performed.
- EDSS, MSFC, MSIS-29 and SF36 assessments will be carried out.
- The study treatment will be infused.

Week 0 +48/72 hours

Patients will have the following performed:

- Concomitant medications will be recorded.
- Adverse events will be recorded.
- The patient will have their vital signs checked.

- An EDSS assessment will be carried out.
- 80mls of blood research samples will be taken.*
- Reading of the Mantoux test.

Week 4 ± 7 days

Patients will have the following performed:

- Concomitant medications will be recorded.
- Adverse events will be recorded.
- The patient will undergo a full physical examination including vital signs.
- Blood will be taken for haematological and clinical chemistry parameter measurement.
- Pregnancy testing will be performed (if applicable).
- 80 ml blood research samples will be taken.*
- Urinalysis will be performed.
- EDSS, T25-FW, MSIS-29 and SF36 assessments will be carried out.
- An MRI will be carried out.

Week 8 ± 7 days

Patients will have the following performed:

- Concomitant medications will be recorded.
- Adverse events will be recorded.
- The patient will have their vital signs checked.
- 80 ml blood research samples will be taken.*

Week 12 ± 7 days

Patients will have the following performed:

- Concomitant medications will be recorded.
- Adverse events will be recorded.
- The patient will undergo a full physical examination including vital signs.
- Blood will be taken for haematological and clinical chemistry parameter measurement.

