12.8 MRI PROCEDURES

12.8.1. Outline

All patients will be scanned at one site: the MS Society-funded 3T MRI scanner at the UCL Institute of Neurology. Scans will be acquired at weeks 0, 4, 12, 24, 28, 36 and 48. If drop-out occurs before the study ends, all remaining MRI scans will be obtained, if possible, at the scheduled time-points or if this will not be possible, at an unscheduled visit (exit visit). The MRIs will be analysed by [name] group at the Institute of Neurology but as the data will also contribute to the international collaborative effort, these MRIs will be anonymised and sent to the Medical Image Analysis Centre (MIAC), located in Basel, Switzerland which is being used for analysis of the primary outcomes.

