12.8.4. Outcome measures

1. Cumulative number of new Gad-enhancing lesions weeks 4-24 inclusive (primary outcome measure to be analysed centrally by [name] group in Basel)
2. Cumulative number of new Gad-enhancing lesions weeks 28 to 48 inclusive
3. Cumulative number of persistent Gad-enhancing lesions weeks 4-24 and 28-48
4. Cumulative number of total Gad-enhancing lesions weeks 4-24 and 28-48
5. Volume of total Gad-enhancing lesions weeks 4-24 and 28-48
6. Cumulative number of new active lesions (new Gad-enhancing and new non-enhancing T2 lesions) weeks 4-24 and 28-48
7. Cumulative number of new and enlarging T2 lesions weeks 12 and 24 compared to baseline (week 0) and weeks 36 and 48 compared to week 24
8. Cumulative number of new T1 hypointense lesions on Gad-enhanced T1-weighted spin echo scans weeks 12 and 24 compared to baseline (week 0) and weeks 36 and 48 compared to week 24
9. Percentage brain volume change (PBVC) on 3D T1-weighted scans at weeks 12 and 24 compared to baseline (week 0) and weeks 36 and 48 compared to week 24
10. Regional atrophy changes in grey matter (using 3D T1-weighted scans and voxel based morphometry) and core white matter structural changes (using advanced diffusion analysis) at weeks 12 and 24 compared to baseline (week 0) and weeks 36 and 48 compared to week 24.
11. Serial analysis including all time points of magnetisation transfer ratio (MTR) measures of non-enhancing T2 lesions present at baseline (week 0)
12. Serial analysis including all time points of MTR measures of non-enhancing T1 hypointense lesions present at baseline (week 0)
13. Serial analysis including all time points of MTR measures of Gad-enhancing lesions present at baseline (week 0)
14. Serial analysis including all time points of MTR measures of new Gad-enhancing lesions that occur during the trial
15. Serial MTR measures at weeks 0, 12, 24, 36 and 48 of normal appearing grey matter
16. Serial MTR measures at weeks 0, 12, 24, 36 and 48 of normal appearing white matter

17. Serial analysis of diffusion-weighted imaging (DWI) data at all time points to assess axonal integrity and structural changes.

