13.3 EVALUATION OF PRIMARY OUTCOME VARIABLES

- Primary outcome: To assess the safety of intravenous therapy with autologous MSCs in MS patients. The safety of MSCs infusion will be evaluated including frequency, timing and severity of any adverse events in both MSCs and placebo treatment groups. A statistical comparison of the number of adverse events between treatment groups will be carried out using a chi-square test.
- Co-Primary outcome: To assess the activity of autologous MSCs in MS patients. The total number of gadolinium-enhancing lesions (GEL) at MRI at week 4, 12 and 24 will be compared between treatment groups using a Negative Binomial (NB) regression analysis, adjusting for the number of GEL at baseline.

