13.6 DATA ANALYSIS

The number of GEL counted over 3 MRI scans will be considered a NB variable and analysed using a NB regression model. The model will be adjusted for the number of GEL on the baseline scan and will include treatment group as covariate. The number of relapses during the study period will be analysed with a NB regression model. Time to event variables will be studied with the Cox proportional-hazards model and visualised using the Kaplan-Meier survival curves. Proportion of events in the two treatment groups will be analysed by the chi-square test.

A paired-data analysis will be run to compare the number of GEL during the placebo and during the treatment arm in the group originally randomised to placebo, using both a parametric mixed model with NB errors and a non-parametric Wilcoxon test.

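### Section 13.4 leaves week 0 GEL out of the combined MRI activity model and week 0 MSFC out of the MSFC comparison as covariates: a minor loss of precision, mainly relevant to pooled data

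*Combined protocol and SAP*

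**What the plan says.** Section 13.3 has the co-primary GEL total over weeks 4, 12 and 24 "compared between treatment groups using a Negative Binomial (NB) regression analysis, adjusting for the number of GEL at baseline". Section 13.6 repeats this directly after naming the GEL count over three scans: "The model will be adjusted for the number of GEL on the baseline scan and will include treatment group as covariate".

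Section 13.4 treats two between-arm secondary outcomes differently:

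- Combined unique MRI activity (new or enlarging T2, enhancing or re-enhancing lesions, same three scans) "will be recorded in the two groups using a Negative Binomial (NB) regression analysis with the treatment group as covariate".
- Mean MSFC change in the MSC group "vs. placebo group compared to baseline will be analysed with a one-way ANOVA test".

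The baseline data exist. Section 12.8.1: "Scans will be acquired at weeks 0, 4, 12, 24, 28, 36 and 48". Section 12.2.1 places the week 0 MRI before infusion and, in the same visit list, "EDSS, MSFC, MSIS-29 and SF36 assessments will be carried out". The composite has no week 0 value of its own, because its T2 part is counted against that scan. Section 12.8.4, item 7, reads "Cumulative number of new and enlarging T2 lesions weeks 12 and 24 compared to baseline (week 0". The baseline lesion covariate to hand is therefore the week 0 GEL count.

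On pooling, section 5.2.4 says "Evaluation of primary and secondary outcomes as well as exploratory outcomes will be carried out at the single national trial level" and goes on to plan the same evaluation on the pooled set of about 160 patients. Section 18 commits only the primary outcomes to pooling and leaves the others to independent analysis.

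**The concern.** The plan treats baseline GEL as worth adjusting for in one negative binomial count over weeks 4, 12 and 24. It then drops it, without a reason, from a second count over the same scans that itself includes enhancing lesions. For MSFC, the change score uses week 0 by subtraction, which fixes the baseline slope at 1 instead of estimating it.

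Sections 6.2 and 13.4 describe the secondary outcomes as preliminary information on efficacy, so the useful product is an estimate with an interval. If baseline values predict the outcome, leaving them out makes that interval wider than it need be.

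**Working it through.** **Inputs from section 13.2.** Control mean GEL over three scans 7.4, SD 11.4; 50% reduction; 80% power at 5%; 160 patients pooled; up to 23 in this trial.

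**Assumptions, because the documents give no figure.** Combined activity borrows the GEL mean, SD and effect. Week 0 GEL explains 10% or 30% of the dispersion. MSFC has equal SDs at both times and baseline correlation ρ = 0.5, 0.7 or 0.9.

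**1. The plan's own figure.** Dispersion k = (11.4² − 7.4)/7.4² = 122.56/54.76 = 2.238. Then

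n per arm = (1.960 + 0.842)² × (1/7.4 + 1/3.7 + 2 × 2.238)/(ln 0.5)² = 7.849 × 4.882/0.4805 = 79.7,

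so 80 per arm and 160 in total (two-sided, 1:1, no dropout assumed). The stated 160 is reproduced, and the negative binomial set-up is a fair base.

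**2. Bias.** In simulation with a true log rate ratio of −0.693, mean estimates at N = 160 were −0.69 to −0.70 with and without baseline GEL. At N = 23 they were −0.66 to −0.72 unadjusted and −0.69 to −0.73 adjusted. For MSFC with a true difference of 0.30, both methods averaged 0.30 to 0.31. Nothing points to bias from leaving the covariate out.

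**3. Count model.** Likelihood-ratio tests, 4,000 simulated trials per cell. Week 0 GEL has mean 7.4/3 and dispersion 2.238. The later total is log-linear in log(week 0 + 1), with residual dispersion 90% or 70% of 2.238. Each cell gives unadjusted → adjusted for the raw week 0 count.

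| N, share explained | SD of log RR | Change in SD | Type I error | Power | Power, size matched to 5% |
|---|---|---|---|---|---|
| 160, 10% | 0.249 → 0.242 | −3% | 0.067 → 0.060 | 0.821 → 0.828 | 0.772 → 0.811 |
| 160, 30% | 0.252 → 0.224 | −11% | 0.075 → 0.054 | 0.841 → 0.885 | 0.796 → 0.875 |
| 23, 10% | 0.688 → 0.714 | +4% | 0.068 → 0.073 | 0.195 → 0.200 | 0.154 → 0.153 |
| 23, 30% | 0.659 → 0.635 | −4% | 0.087 → 0.078 | 0.244 → 0.250 | 0.175 → 0.189 |

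Size-matched power carries about ±2 points of simulation error at N = 160. The SD column is the cleanest measure of precision, because the power columns also reflect how far each test departs from 5%.

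Two cross-checks:

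- Replacing k by 0.9k or 0.7k in the step 1 formula gives a standard error at N = 160 of 0.247 → 0.235 or 0.210 (5% or 15% lower), with power 80.1% → 83.8% or 90.9%. This is more favourable than the simulation, because the formula removes the explained share exactly.
- A second simulation (600 trials per cell) gave both periods a shared patient effect and used log baseline GEL. The unadjusted/adjusted variance ratio was 1.03 to 1.32 at N = 160 and 0.96 to 1.25 at N = 23. The upper ends arose only under the strongest assumed link.

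**4. MSFC.** Per-patient variance is 2σ²(1 − ρ) for change and σ²(1 − ρ²) for ANCOVA, a ratio of (1 + ρ)/2. Allowing for estimation of the slope and one lost degree of freedom,

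width ratio = √[(1 + ρ)/2 × (1 + 1/(N − 4))] × t(N − 3)/t(N − 2).

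| ρ | N = 160 | N = 23 |
|---|---|---|
| 0.5 | 0.869 | 0.891 |
| 0.7 | 0.925 | 0.949 |
| 0.9 | 0.978 | 1.003 |

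At N = 160, where the planned test has 80% power, ANCOVA would have about 90%, 86% and 82%.

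**The case against.** The strongest reply is that nothing in the plan is wrong. The outcomes are secondary and preliminary, the change score already uses week 0 MSFC, and ANCOVA is a preference for efficiency. For this trial the gain is not dependable: at N = 23 the count model is about 4% less precise if the baseline is weakly prognostic, and the MSFC interval is marginally wider at ρ = 0.9. The clear benefit needs a pooled secondary analysis, which section 18 does not promise. Section 5.2.4 describes identical national protocols, so an edit made here alone would break that uniformity. The sizes also rest on a borrowed variance and chosen correlations. All of this stands. It lowers the weight of the point without removing it, since the omission is plain in the text and the pooled gain is real over most of the assumed range.

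Four stronger readings are tempting but not supported:

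- *The unadjusted results are biased.* The design is randomised, and step 2 shows none on average. A chance imbalance among 23 patients can still shift one result. Missing data are a separate question.
- *The unadjusted count test is invalid because its simulated type I error exceeds 5%.* The excess depends on the assumed data generator, and the adjusted test shows it too in most cells.
- *Section 13.6 already extends the adjustment to combined activity.* Its sentence refers to the GEL count named just before it.
- *Week 0 values are unusable because section 12.2.1 lists randomisation at week −10.* They are taken before infusion, with patient, assessors and MRI team blinded (section 9.3), so they remain valid pre-treatment covariates.

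The relapse model in section 13.4 also has treatment group only. It is not examined here.

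**Conclusion.** The point holds as a minor one. Two secondary comparisons omit baseline covariates that the trial collects, and the only consequence shown is lost precision.

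In about 160 pooled patients, adjustment would cut the SD of the log rate ratio by about 3% to 11% and narrow the MSFC interval by about 13% to 2%. In 23 patients the effect is small, nil or slightly negative for the count model (about 4% either way with the raw week 0 count), and from 11% narrower to 0.3% wider for MSFC.

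These sizes assume that combined activity varies as GEL does, that week 0 GEL explains 10% to 30% of its dispersion, and that ρ for MSFC lies between 0.5 and 0.9. The documents give no means of choosing within those ranges. A reader might infer that this trial on its own forfeits useful power, or that adjustment costs nothing. The N = 23 figures support neither.

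**What to change.** - In section 13.4, add the week 0 GEL count to the negative binomial model for combined unique MRI activity, in the same form as in the co-primary model (section 13.6).
- Replace the one-way ANOVA on MSFC change with ANCOVA, with week 0 MSFC as covariate.
- Reconcile sections 5.2.4 and 18 on whether these secondary comparisons are run on the pooled data. If they are, agree the change with the parallel national trials.
- Make the change before efficacy data are unblinded, so that the choice of covariates cannot depend on results.

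Cost: one degree of freedom per model, with a possible slight loss of precision at N = 23 if the baseline is weakly prognostic. The wording sits in the protocol, so the amendment needs the sponsor, ethics and Trust R&D steps in section 16.2. No extra visits, scans or patients are needed.

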13.5 EVALUATION OF EXPLORATORY OUTCOMES*

Patients will undergo biological ‘proof of principle studies’ addressing the effect of MSC treatment on immune responses. Immune parameters will be compared within the patients longitudinally and cross-sectionally between post-MSC vs. post-infusion media treatment time points.

* Only for the patients in the first phase of recruitment

13.6 DATA ANALYSIS

The number of GEL counted over 3 MRI scans will be considered a NB variable and analysed using a NB regression model. The model will be adjusted for the number of GEL on the baseline scan and will include treatment group as covariate. The number of relapses during the study period will be analysed with a NB regression model. Time to event variables will be studied with the Cox proportional-hazards model and visualised using the Kaplan-Meier survival curves. Proportion of events in the two treatment groups will be analysed by the chi-square test.

A paired-data analysis will be run to compare the number of GEL during the placebo and during the treatment arm in the group originally randomised to placebo, using both a parametric mixed model with NB errors and a non-parametric Wilcoxon test.

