13. STATISTICS AND DATA ANALYSIS

13.1 RATIONALE

The main aim of each national trial participating in this international collaborative effort, including the present one, is to assess the feasibility, safety and the toxicity of MSC infusion, as administered within this specific treatment protocol, in active MS. To fulfill this aim, all randomised patients receiving at least one MSCs infusion (or infusion media) will be followed for at least two years after the last study drug administration. All adverse events will be recorded and compared in the two treatment groups. Comparative analyses of the incidence of new GEL at MRI acquired on conventional 1.5 T MRI scans over 24 weeks will be conducted as well, to provide preliminary data on the activity of the experimental treatment. However, the main analyses of safety, toxicity and activity will be those on the entire data set obtained by pooling the results of all national trials, for an expected total of 160 randomised patients.

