13.2 SAMPLE SIZE

Up to 23 patients are expected to be enrolled in the clinical trial for evaluation of the primary outcome (safety). Data from this clinical trial and from all other national trials will be pooled together for efficacy evaluation which will be evaluated as a decrease in the number of GEL (co-primary outcome).

A sample size of 160 patients was estimated to give an 80% power at a significance level of 5% to detect a decrease of 50% in the number of GEL counted during the 6 months duration of treatment. This number was estimated assuming that the average number of total GEL on 3 MRI scans (scan at weeks 4, 12 and 24) will be 7.4 (SD=11.4), that is half of the number of total number of GEL counted over 6 monthly scans in the phase 2 study of oral fingolimod for MS [43] .

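### The planned lesion-count model has no term for national trial, although the main activity analysis pools at least seven national trials; what may be lost is precision, not validity

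*Combined protocol and SAP*

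**What the plan says.** One model is given for the between-group GEL comparison. Section 13.6 states: "The model will be adjusted for the number of GEL on the baseline scan and will include treatment group as covariate". Section 13.3 and the Study Summary describe the same analysis: "using a Negative Binomial (NB) regression analysis, adjusting for the number of GEL at baseline". None of these places mentions national trial, country or scanner. The mixed NB models in 13.4 and 13.6 serve comparisons over time within a randomised group, and no trial effect is mentioned there either. Section 13.6 does not say whether its model is meant for the UK data, the pooled data, or both.

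On the data set, 13.1 says that "the main analyses of safety, toxicity and activity will be those on the entire data set obtained by pooling the results". Section 13.2 sends the efficacy evaluation to the pooled data, and section 18 pools the primary outcomes. Section 5.2.4 says: "Identical, parallel but independent national trials will be conducted in Spain, Sweden, Denmark, France, Germany and Canada". With the UK trial that makes at least seven.

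The design target in 13.2 is 160 pooled patients for 80% power at the 5% level "to detect a decrease of 50% in the number of GEL counted during the 6 months duration of treatment", assuming a mean of 7.4 lesions (SD 11.4) over three scans. The UK trial contributes up to 23 patients. Adverse events are compared by a chi-square test with no stratum (13.3).

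On imaging, 13.1 speaks of lesions on scans "acquired on conventional 1.5 T MRI scans", whereas 12.8.1 places all patients on "the MS Society-funded 3T MRI scanner at the UCL Institute of Neurology".

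**The concern.** Separately run trials can differ in underlying lesion rate through referral patterns, disease mix or image acquisition. If the pooled model ignores this, the between-trial part of the variation goes into the residual dispersion, and chance imbalance of treatment across trials adds noise to the rate ratio. The pooled model matters because the UK trial alone cannot answer the efficacy question (see the working). If the term is not prespecified, whether to include it also becomes a choice that could be made after the results are known.

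**Working it through.** **1. The plan's own figure.** Inputs from 13.2: control mean 7.4, SD 11.4, rate ratio 0.5 (treated mean 3.7). Assumed because not stated: 1:1 allocation, two-sided 5%.

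- NB dispersion: (11.4² - 7.4)/7.4² = 122.56/54.76 = 2.238.
- Patients per arm: (1.960 + 0.842)² × (1/7.4 + 1/3.7 + 2 × 2.238)/(ln 0.5)² = 7.849 × 4.882/0.4805 = 79.7, so 80 per arm and 160 in total. Power at 160 is 80.1%.

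The stated 160 therefore reproduces, from a formula with one dispersion and no trial component. The same formula with 23 patients (11.5 per arm) gives about 18.5% power, so the pooled analysis carries the efficacy conclusion.

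**2. The missing input.** The documents give no SD of the log lesion rate between trials. Values of 0 to 0.75 were assumed. For scale, 95% of trials would lie within a factor exp(1.96 × SD) of the average: 1.6 at 0.25, 2.7 at 0.5 and 4.3 at 0.75.

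**3. Power with and without six trial indicators, baseline GEL left out.** Seven trials (six of 23 and one of 22, total 160), dispersion 2.238 taken as within-trial, 1000 runs per row, Monte Carlo error about 1.3 points.

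| Between-trial log SD | Allocation stratified by trial | Power without term | Power with term | Change (points) |
|---|---|---|---|---|
| 0 | no | 80.9% | 79.8% | -1.1 |
| 0 | yes | 80.1% | 79.8% | -0.3 |
| 0.25 | no | 76.9% | 77.0% | +0.1 |
| 0.25 | yes | 78.6% | 79.9% | +1.3 |
| 0.5 | no | 74.0% | 79.3% | +5.3 |
| 0.5 | yes | 74.9% | 80.0% | +5.1 |
| 0.75 | no | 70.2% | 77.7% | +7.5 |
| 0.75 | yes | 70.3% | 77.3% | +7.0 |

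The mean estimate of the rate ratio was 0.495 to 0.504 in every row, with and without the term.

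**4. The same with baseline GEL in both models, as planned.** Half of the patient-level frailty was assumed shared between baseline and follow-up; 500 runs per setting, Monte Carlo error about 1.7 points; ranges cover stratified and unstratified allocation and raw or log baseline.

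- Log SD 0 to 0.25: change of -1 to +2 points.
- Log SD 0.5: from about 80% to 83-84%.
- Log SD 0.75: from 75-78% to 79-84%.

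Baseline GEL absorbs some of the difference but not all of it. Taking steps 3 and 4 together and allowing for Monte Carlo error, the rounded ranges are about -1 to +2 points (0 to 0.25), +2 to +5 (0.5) and +2 to +7 (0.75).

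**5. A control at zero.** With baseline GEL in both models, the variance of the log ratio fell by about 16% at log SD 0.5 and by 16-23% at 0.75 in one set-up. It also fell by 7-8% in that set-up when the between-trial SD was zero. Without baseline GEL (step 3, unstratified), the empirical SD at zero instead rose from 0.249 to 0.262. The percentage cut in variance thus depends on the set-up, and not all of it can be credited to between-trial variation.

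**6. Field strength.** Section 13.1 covers each national trial including this one, and describes 1.5 T scans. Section 12.8.1 has every UK patient scanned at 3 T. Both cannot hold for the UK data.

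**The case against.** The case against has several parts.

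- **The 13.6 model is not labelled pooled.** This is a UK protocol with one scanning site, and a national-trial term cannot be estimated in it. That is right. But 13.1 makes the pooled analysis the main one, and no other model is offered for it, so the point applies when this model is used on the pooled data.
- **Heterogeneity may be small.** The trials are to share a protocol and entry criteria (5.2.4), and the primary lesion count is read at one centre (12.8.1, 12.8.4). This stands as a reason to expect a log SD nearer the low end, where the gain is negligible. Central reading does not make patients or scanners alike.
- **The size depends on how the SD of 11.4 is read.** The tables above take it as within-trial. If total dispersion is held fixed instead, a rebuilt simulation with baseline GEL showed a gain of about 1 point at each setting. That stands too.

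A reader might go further and infer three things that the documents do not support. First, that patients are randomised within country: sections 9.2, 14.2 and 17 describe one central web system and neither state nor exclude stratification by country. Second, that the 1.5 T and 3 T statements show scanners differing between countries: the conflict lies inside this protocol and says nothing firm about the other trials. Third, that the test is invalid: simulated type I error was 4.3-8.9% without the term and 6.3-8.5% with it, which shows no clear difference.

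**Conclusion.** The point holds as a matter of precision. The main activity analysis pools at least seven independent trials, and the one GEL model given has no term for them. The rate ratio is not biased on average, and 160 is not wrong on its own inputs. The gain from the term is negligible at a between-trial log SD of 0.25 or below and a few power points at 0.5 to 0.75. It rests on an assumed SD, seven trials of about equal size, 1:1 allocation and the dispersion implied by 13.2. Estimates with and without the term differed by about 0.03 to 0.13 on the log scale on average, so settling the choice in advance has value of its own. No calculation was made for the adverse-event comparison; stratifying it rests on the same reasoning only. The field-strength conflict is real but separate, and is not evidence for a trial term.

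**What to change.** 1. In 13.3 and 13.6, state that when the NB model for GEL is applied to the pooled data it will include national trial as a fixed factor or stratum, in addition to treatment and baseline GEL.
2. State that the pooled adverse-event comparison will be stratified by national trial in the same way.
3. State in 9.2 whether randomisation is stratified by national trial.
4. Reconcile the field strength in 13.1 with that in 12.8.1.

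The cost is six parameters in 160 patients, at most about 1 power point if the trials do not differ, and a few sentences. No extra patients or data are needed. The pooled model should be agreed with the other national trials before unblinding.
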